In 2019, Alzheimer’s Disease International estimated that there were over 50 million people living with dementia globally, a figure set to increase to 152 million by 2050 [1]. Alzheimer’s disease (AD) is the most common type of dementia in older people, characterized by early accumulation of amyloid beta (A β) in the brain, which triggers tau pathology, synaptic loss, and neuronal death. These processes ultimately lead to cognitive decline and dementia. Recent advances have produced disease-modifying therapies such as aducanumab [2], lecanemab[3], and donanemab [4], which promote amyloid clearance and may provide clinical benefit. However, their long-term safety remains uncertain, and their high cost limits accessibility, particularly in countries such as China. For most patients, treatment remains focused on symptomatic therapy with two classes of FDA-approved drugs: cholinesterase inhibitors (donepezil, rivastigmine, galantamine) for mild to moderate AD, and the N-methyl-D-aspartate–receptor antagonist memantine for moderate to severe disease. Higher doses of cholinesterase inhibitors may improve symptoms in advanced stages but are often poorly tolerated due to cholinergic side effects, including nausea, vomiting, and diarrhea [5,6]. There remains a pressing need for both safer symptomatic options and affordable disease-modifying strategies.

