- 1) To evaluate if adding acupuncture to donepezil improves outcomes in patients with mild AD;
- 2) If there is an effect of acupuncture, whether the previous effect of acupuncture treatment is present after washout;
- 3) If acupuncture has a long-term effect on AD, is it related to changes in gut microbiota?

3 Study design

This is a prospective, randomized, participant-masked, sham-controlled trial, with each eligible participant randomly assigned to either active or sham acupuncture added to donepezil treatment. All participants or their legal representatives will provide written informed consent and be treated in accordance with the tenets of the Declaration of Helsinki (version 2013).

Table 1 Trial summary

Title	An efficacy and safety trial of acupuncture as adjunct to donepezil in patients with mild AD
Clinical indication	Treatment of mild AD
Trial type	Interventional
Type of control	Sham/Placebo
Route of intervention	needle stimulation + oral
Trial blinding	Single-blind
Treatment groups	Active acupuncture for 14 weeks
	Sham acupuncture for 14 weeks
Concomitant therapy	Donepezil 5 mg QD for 28 weeks
Number of trial subjects	160 in total
Estimated duration of trial	The sponsor estimates that the trial will require approximately 2.5 years from the time the first participant signs the informed consent until the last participant's last visit.
Duration of participation	Each participant will participate in the trial for approximately 30 weeks from the time the participant signs the Informed Consent Form through the final contact. After a screening phase, each subject will receive assigned treatment for 28 weeks. After the end of treatment each participant will be followed for at least 14 days.
Randomization ratio	1:1

4 Methodology

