4.1 Participant recruitment

The study will take place in the Outpatient Department, Shanghai Research Institute of Acupuncture and Meridian, Shanghai, China. The recruitment will be announced via our official account on social media and forwarded once a month. Placement of brochures and study posters in Yueyang Hospital of Integrated Traditional Chinese and Western Medicine, Shanghai University of Traditional Chinese Medicine and Ruijin Hospital, Shanghai Jiaotong University School of Medicine (collaborating hospitals) and community centers will be used to assist recruitment. In addition, we conducted disease-related science lectures in the elderly community and put up posters in the community to further promote the recruitment. Participants or their representatives will be instructed to read the informed consent and those who showed interest in the study will be scheduled for the screening visit. After presenting written informed consent, participants will be examined, and if all entry criteria are met, will commence a 4-week run-in period of treatment with donepezil hydrochloride (5 mg/capsule, China) 5 mg daily (prior AD treatments will be terminated by then). To further avoid potential confounding effects on the clinical outcomes and gut microbiota, participants will be instructed to maintain their regular diet and activity level, and refrain from probiotics, prebiotics, or synbiotics use. Upon successful completion of the 4-week run-in, participants will be scheduled to complete baseline assessments and undergo randomization. The study flowchart and proposed trial schedule are shown in Figure 1 and Table 1, respectively.

[figure not shown]

Figure 1 Flow diagram of the study protocol

Table 2 Study schedule

Visit No.	V1	V2	V3	V4	V5	V6
End of Week Relative to Study Treatment Start	-4	0	7	14	21	28
Tolerance Interval for Visit (d)	0	0	±3	±3	±7	±7
Entry and Administrative						
Eligibility	X	X				
Informed consent	X					
Physical/neurological examination	X					X
Demographics	X					
Medical history	X					
Randomization		X				
Interventions						
Active/Sham acupuncture						
Donepezil						
Outcomes Measures						
ADAS-cog12		X	X	X	X	X
MMSE		X	X	X	X	X
ADCS-ADL		X	X	X	X	X
NPI		X	X	X	X	X
Fecal samples collection		X		X		X
Additional Assessment						
Adverse events						
Treatment compliance						

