4.9 Statistical analysis

All analyses were pre-specified in a statistical analysis plan finalized before database lock. The primary analysis followed a modified intention-to-treat (mITT) principle, including all randomized participants with at least one post-baseline efficacy assessment. A per-protocol (PP) analysis was performed as a sensitivity analysis, excluding participants with major protocol deviations (<85% intervention adherence or violation of inclusion criteria). Changes from baseline in ADAS-cog12 scores were analyzed using linear mixed-effects models (LMMs) with repeated measures. The models included fixed effects for treatment group (active vs. sham), time, and their interaction, as well as sex, AD drug use history and TCM pattern; age, years of education, time since diagnosis, and baseline ADAS-cog12 score were included as covariates. A random intercept for each participant was used, with an unstructured covariance matrix. MMSE, ADCS-ADL23, and NPI outcomes were analyzed using the same model structure. Pre-specified subgroup analyses were conducted by TCM pattern, age, sex, and education levels. Continuous outcomes were summarized as means with 95% confidence intervals (CIs). The LMM framework accommodated missing data under the missing-at-random assumption. In addition, multiple imputation using fully conditional specification was conducted for primary and key secondary endpoints as sensitivity analyses. All statistical tests were two-sided with a significance threshold of 0.05. Analyses were performed using SAS software, version 9.4 (SAS Institute, Cary, NC, USA).

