16S rRNA gene sequencing analysis are performed using QIIME and R packages (v3.2.0). OTU-level alpha diversity indices are calculated using the OTU table in QIIME. OTU-level ranked abundance curves are calculated to assess OTUs richness and evenness among samples. Beta diversity analysis will be performed to investigate the structural variation of microbial communities across samples using UniFrac distance metrics and visualized via PCoA. The linear discriminant analysis (LDA) effect size method is used to characterize the taxa with statistical significance and biological relevance. The set value of the LDA score is 2. Partial least-squares-latent structure discriminate analysis is performed using Simca-P 14.0 (Umetrics AB, Sweden) to observe the fecal microbiota pattern in different groups based on OTUs of the sequencing data from each sample. Variables with variable importance in projection >1 are identified as important contributors to generation of the model. The functional profile of KEGG

Orthology for each sample will be predicted from 16S rRNA amplicon data with Phylogenetic Investigation of Communities by Reconstruction of Unobserved States. To test the overall correlation between changes in microbiome and altered outcome variables, pairwise Spearman's rank correlations within the active and sham acupuncture groups at baseline, 14 and 28 weeks are calculated and adjustments are performed using the Benjamini–Hochberg procedure and Spearman rho values are filtered with a false discovery rate at 5%.

5 Trial monitoring

An independent DSMB is established to review accumulating study data on a periodic basis and make recommendations to protect the safety of the participants. The members of the DSMB include a recognized expert in the field of AD, a senior acupuncturist, and a statistician. All members are external to our institute. Only the DSMB is authorized to evaluate unblinded interim efficacy and safety analyses. An interim analysis is proposed to be conducted after approximately 50% of participants had completed the week 14 assessments. According to the Haybittle–Peto stopping guideline, the trial would be considered for early termination only if the interim analysis demonstrated overwhelming evidence of efficacy ($P < 0.001$) or raised serious safety concerns based on recommendations from the independent Data and Safety Monitoring Board (DSMB). Otherwise, the study would continue as planned until the final analysis.

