Appendix 1 Protocol revised history

Protocol revised history-V2.0

- 1) P11 The model of electroacupuncture apparatus was revised from SDZ-V to SDZ-III.
- 2) P18 The score of Clinician's Interview-Based Impression of Change with caregiver input (CIBIC plus) was removed from the secondary outcome, and the score of Neuropsychiatric Inventory (NPI) was added.

Protocol revised history-V3.0

- 1) P21-4.8 The original sample size of 143 cases considering 10% dropout rate was revised to 160 cases considering 20% dropout rate.

Protocol revised history-V4.0-30/9/2022 (after the trial started)

- 1) P21-4.9 Time since diagnosis and AD drug use history were added as fixed effects in the model (reason: It was originally thought that more than 95% of AD patients used drugs, but it was found that the rate of drug use in mild AD was not so high, so this confounding factor was taken into account in the statistics). Additionally, the original method for handling missing data in sensitivity analysis, last observation carried forward (LOCF) method, was revised to multiple imputation (MI) method (reason: reduce the risk of bias).

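### The only planned analysis linking gut microbiota to clinical outcome (Objective 3) is an unadjusted within-arm correlation, which randomisation does not protect from shared causes

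*Protocol*

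**What the plan says.** Objective 3 in Protocol section 2 asks: "If acupuncture has a long-term effect on AD, is it related to changes in gut microbiota". The analysis that answers it is at the end of Protocol 4.9. Its stated purpose is "To test the overall correlation between changes in microbiome and altered outcome variables", and its method is pairwise Spearman correlation: "rank correlations within the active and sham acupuncture groups at baseline, 14 and 28 weeks are calculated". P values are adjusted by Benjamini-Hochberg at a 5% false discovery rate. No covariate, partial correlation or regression is mentioned. The other microbiota methods in 4.9 (diversity indices, LDA effect size, discriminant analysis, predicted function) do not relate microbiota to clinical scores. The SAP shows faecal sampling in its visit schedule (3.7) but plans no microbiota analysis.

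The clinical model in the same section does adjust, "as well as sex, AD drug use history and TCM pattern; age, years of education, time since diagnosis", and for baseline ADAS-cog12. It covers only ADAS-cog12, MMSE, ADCS-ADL23 and NPI. AD drug use history entered that model in version 4.0 because prior drug use was lower than expected, "so this confounding factor was taken into account in the statistics" (Protocol Appendix 1). Every participant who meets the entry criteria "will commence a 4-week run-in period of treatment with donepezil hydrochloride" before baseline (Protocol 4.1).

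**The concern.** Randomisation balances patient characteristics between arms. It does nothing for an association between two measured variables inside one arm. The plan therefore adjusts where randomisation already prevents systematic confounding, and leaves out adjustment where confounding is possible. A variable that influences both the abundance of a taxon and a cognitive score can create a correlation with no direct link behind it. If its two effects have opposite signs to a true link, it can hide that link. Age, sex, baseline severity and AD drug use history are plausible candidates, and all are recorded at baseline (SAP 5.5).

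The entry rules and instructions on diet, probiotics, antibiotics and bowel disease (Protocol 4.1 and 4.2.2) do not address these four variables. The Benjamini-Hochberg step limits chance findings among many tests. It does not separate a direct association from one due to a common cause. At stake is the reading of Objective 3, where a shared-cause correlation in the active arm could be taken as support for an acupuncture-gut-AD axis.

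**Working it through.** **Numbers per arm.** Protocol 4.8 gives 80 randomised per arm and 128 completers in total, so 64 per arm. This reproduces: with a difference of 3.0 and SD 6.0, a two-sample t-test needs 64 per arm for 80% power (power 0.801), and 128/0.8 = 160. No sample size is stated for the correlations, so 64 to 80 per arm is used below.

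**Assumptions, because the documents give no figures.** A share p = 0.3 to 0.5 of an arm has no prior AD drug. Drug history shifts both a taxon and the outcome by d = 0.5, 0.8 or 1.0 within-group SD. There is no direct link between taxon and outcome.

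**Induced correlation.** Each variable has variance 1 + p(1-p)d² and their covariance is p(1-p)d², so r = p(1-p)d² / [1 + p(1-p)d²].

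- d = 0.5: p = 0.3 gives 0.0525/1.0525 = 0.050; p = 0.5 gives 0.0625/1.0625 = 0.059.
- d = 0.8: 0.1344/1.1344 = 0.118; 0.16/1.16 = 0.138.
- d = 1.0: 0.21/1.21 = 0.174; 0.25/1.25 = 0.200.

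**Per-pair false-positive rate at two-sided 0.05.** Using Fisher's z with variance 1.06/(n-3), the standard error is √(1.06/61) = 0.132 at n = 64 and √(1.06/77) = 0.117 at n = 80. The rate is Φ(z/SE - 1.96) + Φ(-z/SE - 1.96), with z = atanh(r). The low end is n = 64, p = 0.3; the high end is n = 80, p = 0.5.

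| Shift in both variables | Approximation, low to high | Simulation |
|---|---|---|
| 0.5 SD | 7% to 8% | 7-8% |
| 0.8 SD | 15% to 22% | 15-22% |
| 1.0 SD | 26% to 41% | 26-43% |

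Partial Spearman, conditioning on drug history, brings every case back to about 5% (4.6-5.4%).

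**After Benjamini-Hochberg at 5%.** Simulation for one arm at one visit, with 100 taxa of which 20 are affected:

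| Shift in both variables | At least one taxon passes | A given affected taxon passes |
|---|---|---|
| 0.5 SD | 6-9% | 0.1-0.2% |
| 0.8 SD | 12-22% | 0.5-1.6% |
| 1.0 SD | 31-58% | 3-9% |

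Repeat runs move the middle column by about three percentage points at most.

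**A second parameterisation.** Take a continuous shared cause correlated 0.3, 0.4 or 0.5 with both variables, n = 64, and 100 taxa of which 30 are affected. At least one taxon passes in 11%, 29% and 68% of runs unadjusted, and in 4.5-7% after adjustment. At a correlation of 0.2 the per-pair rate is only 6.0%, against a nominal 5%.

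**The case against.** The strongest reply is that the drug-history route is speculative and the material inflation needs strong confounding. Much of this stands.

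- **Size of the shifts.** On the protocol's SD of 6.0, a shift of 0.5 SD is 3.0 points, the whole assumed acupuncture effect. Shifts of 0.8 and 1.0 SD are 4.8 and 6.0 points. No document supports effects that large for drug history alone, and all patients share the same 4-week run-in. If only 15% of an arm is drug-naive, the chance of any Benjamini-Hochberg hit at n = 64 is about 6%, 8% and 12%. However, age and severity are not handled by the run-in, and shared causes acting in the same direction add up.
- **Donepezil and the gut.** A reader might infer that newly started donepezil will create a false acupuncture-gut-cognition link, and that the plan itself names the confounder. The documents do not go that far. The phrase "often poorly tolerated due to cholinergic side effects, including nausea, vomiting, and diarrhea" in the protocol's background concerns tolerability at higher doses, not microbiota. The confounding remark in Appendix 1 concerns the efficacy model. Carrying either over to the microbiota is an inference.
- **Change scores.** If changes are correlated, stable level differences drop out and only factors driving both changes remain. This reduces the problem but does not remove it. The wording is ambiguous, and a baseline correlation cannot use change from baseline, so at least that set is on levels.
- **Baseline and sham correlations as a check.** A shared-cause link should tend to appear there too. This helps interpretation, but 4.9 specifies no comparison between arms or visits.
- **Exploratory status.** Microbiota is not among the outcomes in SAP 6.1, and Objective 3 asks only about a relation. That limits the weight of the point, but the correlation still carries a numbered objective.

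**Conclusion.** The point holds as a weakness of method in a supporting objective. The only planned link between microbiota and outcome is unadjusted within each arm, neither randomisation nor Benjamini-Hochberg guards against shared causes, and the variables needed to adjust are already collected.

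Its size depends on confounder strength, which the documents do not give. At 0.5 SD the inflation is slight. At 1.0 SD it is large, with roughly a one-in-three to better-than-even chance of at least one spurious taxon per arm and visit. These figures rest on the assumed 30-50% drug-naive share, 100 taxa with 20 affected, and equal shifts in both variables.

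A reader might conclude that a taxon marking recent donepezil start would pass the 5% filter and be reported. The same calculation contradicts this, since any single affected taxon passes in under 10% of runs even at 1.0 SD. Nor does the point bear on the comparison of active with sham acupuncture on ADAS-cog12 or the other clinical scales.

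**What to change.** In Protocol 4.9, and mirrored in the SAP, report partial Spearman correlations (correlating rank residuals) as follows:

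- Adjust for AD drug use history, age and sex at all three time points.
- Adjust also for baseline ADAS-cog12 at weeks 14 and 28 only. At baseline it is itself the outcome: its residuals would be zero and the partial correlation undefined. For baseline MMSE it would remove much of the cognitive signal.
- Apply Benjamini-Hochberg to the partial-correlation P values.
- Keep the unadjusted coefficients as a supplementary table.
- Describe the results as associational, since unmeasured shared causes remain possible.

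The cost is 3 degrees of freedom at baseline and 4 at weeks 14 and 28, out of about 62 per arm (64 - 2), plus a little more analysis work. No new data are needed.

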Appendix 1 Protocol revised history

Protocol revised history-V2.0

- 1) P11 The model of electroacupuncture apparatus was revised from SDZ-V to SDZ-III.
- 2) P18 The score of Clinician's Interview-Based Impression of Change with caregiver input (CIBIC plus) was removed from the secondary outcome, and the score of Neuropsychiatric Inventory (NPI) was added.

Protocol revised history-V3.0

- 1) P21-4.8 The original sample size of 143 cases considering 10% dropout rate was revised to 160 cases considering 20% dropout rate.

Protocol revised history-V4.0-30/9/2022 (after the trial started)

- 1) P21-4.9 Time since diagnosis and AD drug use history were added as fixed effects in the model (reason: It was originally thought that more than 95% of AD patients used drugs, but it was found that the rate of drug use in mild AD was not so high, so this confounding factor was taken into account in the statistics). Additionally, the original method for handling missing data in sensitivity analysis, last observation carried forward (LOCF) method, was revised to multiple imputation (MI) method (reason: reduce the risk of bias).

**Efficacy and safety of acupuncture adjunct to donepezil in patients with
mild Alzheimer's disease: a randomized, sham-controlled trial
(NCT05078944)**

**Shanghai Research Institute of Acupuncture and Meridian
Shanghai University of Traditional Chinese Medicine**

**Statistical Analysis Plan (SAP)
Version 4.0-30/9/2022**

1 Administrative Information

SAP version

4.0-30/9/2022

Protocol version

4.0

SAP revisions

SAP revised history-V2.0

6.1 The score of Clinician's Interview-Based Impression of Change with caregiver input (CIBIC plus) was removed from the secondary outcome, and the score of Neuropsychiatric Inventory (NPI) was added.

SAP revised history-V3.0

3.3 The original sample size of 143 cases considering 10% dropout rate was revised to 160 cases considering 20% dropout rate

SAP revised history-V4.0

6.2 Time since diagnosis and AD drug use history were added as fixed effects in the model (reason: It was originally thought that more than 95% of AD patients used drugs, but it was found that the rate of drug use in mild AD was not so high, so this confounding factor was taken into account in the statistics). Additionally, the original method for handling missing data in sensitivity analysis, last observation carried forward (LOCF) method, was revised to multiple imputation (MI) method (reason: reduce the risk of bias).

Roles and responsibility

Name	Affiliation	Role
[name]	Shanghai Research Institute of Acupuncture and Meridian, Shanghai University of Traditional Chinese Medicine, Shanghai, China	Person writing the SAP
[name]	Shanghai Institute of Traditional Chinese Medicine for Mental Health, Shanghai, China	
[name]	Department of Biostatistics, School of Public Health, Fudan University, Shanghai, China	Senior statistician responsible
[name]	Shanghai Research Institute of Acupuncture and Meridian, Shanghai University of Traditional Chinese Medicine, Shanghai, China	Chief investigator

2 Introduction

2.1 Background and rationale

Preclinical studies suggest acupuncture may offer symptomatic relief or modify disease progression in Alzheimer's disease (AD), yet clinical evidence remains limited.

2.2 Objectives

This study evaluated whether adding acupuncture to donepezil improves outcomes in patients with mild AD and whether any benefits persist after treatment ends.

3 Study Methods

3.1 Trial design

This is a prospective, randomized, parallel (1:1), sham-controlled trial, with each eligible participant randomly assigned to either active or sham acupuncture added to donepezil treatment.

3.2 Randomization

The randomization sequence is generated by a third party in permuted blocks of randomly varying sizes (4 and 6) using the 'proc plan' procedure of the SAS 9.4. Consecutively numbered opaque sealed envelopes for each group are stored in a secure location and opened sequentially upon enrollment of a study participant by the research assistant.

3.3 Sample size

Sample size was estimated using SAS version 9.4, with ADAS-cog12 at week 14 as the designated primary outcome measure. Based on the results of previous studies, we assume a treatment difference of approximately 3.0 with a standard deviation of 6.0. Considering a 10% non-adherence to treatment and a 10% loss to follow-up, 80 randomized patients per arm or 160 randomized patients in total (128 completers), will have more than 80% power and a type I error rate of 5% for the ADAS-cog12 comparison to detect a significant treatment difference.

